PROTOCOL TITLE: Visual Outcomes and Patient Satisfaction with Bilateral PanOptix Versus Bilateral Synergy

PROTOCOL # 69881171

STUDY TREATMENTS: Non-interventional (None).

Background:

The Tecnis Synergy IOL has a claim to allow patients to experience continuous high-contrast vision from far through near even in low-light conditions.

A J&J-sponsored post marketing study done outside of the US claim superiority of range of vision for the Tecnis Synergy IOL over the PanOptix IOL

Clinical Hypothesis:

Patients with bilateral Panoptix IOLs have non-inferior distance, intermediate, and near visual acuity compared to patients with Synergy IOLs in both photopic and mesopic conditions with less glare, haloes, and/or starbursts.

Scientific Rationale:

The Synergy IOL is a combination of two previous technologies, the ZLB00 and the ZXR00, into a single IOL. Each had relatively significant rates of glare and halos, and the inference is that the Synergy IOL has a similar glare profile. There is a need to look at patient visual outcomes and the visual disturbance profile comparing trifocal technology with combined EDOF/Bifocal technology in the United States

Study Objectives:

The objective of this study is to test the hypothesis that bilateral Panoptix patients targeted corrected at plano sphere OU will have non-inferior distance, intermediate, and near vision compared to patients with bilateral Synegy IOL with fewer complaints of glare, halos, or starbursts as quantified by a survey.

The objective will be completed by measuring binocular corrected visual outcomes at distance, intermediate, and near when at plano sphere.

In addition, the patients will also fill out a questionnaire to determine their level of satisfaction.

OVERALL STUDY DESIGN

This is a non-interventional prospective, single center, bilateral, examiner blinded, two-arm comparative study of the outcomes for patients following successful, uncomplicated cataract surgery performed by 4 surgeons using similar surgical techniques. 155 subjects will be enrolled in each arm of the study, with 310 total subjects. All patients will have had bilateral implantation of a Synergy IOL (DFR00/DFW***) or Panoptix IOL (TFAT*0) at the time of uncomplicated cataract surgery.

Duration:

3 months or longer to meet required enrollment.

Administration:

Patients with healthy eyes who meet the inclusion criteria and have had bilateral Synergy IOLs or Panoptix IOLs implanted at the time of cataract surgery will be offered the opportunity to participate in the study.

Visit Schedule:

All subjects will undergo 1 visit. At the study visit and after informed consent, the subjects' demographic information will be collected, and the subject will have the following testing:

- 1) Manifest refraction
- 2) Distance corrected binocular distance, intermediate (60 cm), and near (40 cm and 33 cm) visual acuity
- 3) Uncorrected binocular distance, intermediate (60 cm), and near (40 cm) visual acuity visual acuity
- 4) Patient survey regarding satisfaction and glare, halos, starbursts using IOLSAT and QUVID questionnaires, respectively
- 5) Binocular defocus curve (+1.00 D to -4.00 D, 0.5 D steps)
- 6) Halo and Glare testing using VS Halo & Glare
- 7) Self-reported visual disturbance questionnaire

STUDY POPULATION CHARACTERISTICS:

Condition

Patients with healthy eyes and uncomplicated bilateral implantation of Panoptix IOLs or Synergy IOLs.

Number of Subjects:

Under the assumption that the difference between binocular targeted corrected distance, intermediate, and near visual acuity between the two arms greater than 0.05 logMAR, thus demonstrating superiority, then 155 patients per arm would be required, for a total of 310 patients. The standard deviation for each measurement is 0.15 logMAR, a power of 80% and Type I error probability of 0.05.

Source: Kohn MA, Senyak J. Sample Size Calculators [website]. UCSF CTSI. 8 August 2021. Available at https://www.sample-size.net/ [Accessed 28 October 2021]

Inclusion/Exclusion Criteria (all study criteria apply to each study eye unless otherwise indicated):

Inclusions

- 1) Adults, 40 years of age having already undergone cataract removal by phacoemulsification with a clear corneal incision in both eyes
- 2) Implantation of bilateral Synergy IOLs (DFR00/DFW***) or bilateral Panoptix IOLs (TFAT*0), toric or non-toric
- 3) Able to comprehend and willing to sign informed consent and complete all required testing procedures
- 4) Best Corrected Distance Visual Acuity (BCDVA) projected to be 0.10 logMAR (Minimum Angle of Resolution) or better
- 5) Clear intraocular media
- 6) Minimum of two weeks post YAG capsulotomy to treat PCO
- 7) Residual refractive astigmatism ≤ 0.75 diopters
- 8) Post-operative refractive spherical equivalent from +0.50 to -0.50 SE

Exclusions

Subjects will not be permitted to enroll in this study if they meet any of the following exclusion criteria:

- 1) Any corneal abnormality, other than regular corneal astigmatism (as determined by preoperative testing) that in the opinion of the investigator would confound the outcome(s) of the study
- 2) Any complication during cataract surgery (capsular tear, vitrectomy, etc)
- 3) History of or current retinal conditions or predisposition to retinal conditions
- 4) Amblyopia or strabismus in either eye
- 5) History of or current anterior or posterior segment inflammation of any etiology
- 6) Any form of neovascularization on or within the eye
- 7) Glaucoma (uncontrolled or controlled with medication)
- 8) Optic nerve atrophy
- 9) Subjects with diagnosed degenerative eye disorders
- 10) Postoperative CDVA worse than 0.10 logMAR in either eye.

11) Subjects who have an acute or chronic disease or illness that would confound the results of this investigation in the opinion of the principal investigator (e.g. immunocompromised, connective tissue disease, clinically significant atopic disease, etc)

EVALUATION CRITERIA:

The main objective of this study is to demonstrate superiority of distance, intermediate, and near vision with bilateral Panoptix IOLs compared to bilateral Synergy IOLs in both photopic and mesopic conditions with less glare, haloes, and/or starbursts.

Primary Clinical Endpoints:

Binocular DCNVA of Trifocal (Alcon PanOptix) versus EDOF/Bifocal (Johnson and Johnson Tecnis Synergy) at 40 cm.

Secondary Exploratory Clinical Endpoints

Patient self-reported visual disturbances

QUVID questionnaire (Percentage of subjects not bothered by halos)

Binocular BCDVA and DCIVA (60 cm)

Binocular UCDVA, UCIVA (60 cm), UCNVA (40 cm)

Patient reported satisfaction by IOLSAT

Binocular defocus curve

Post-op refraction

Exploratory:

Spectacle independence (IOLSAT)

Halo and Glare reported using VS Halo & Glare (visu-med.com)

Binocular DCNVA (33 cm)

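### The stated hypothesis is non-inferiority, but the sample size and main objective are superiority, and no margin or testing order connects them

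*Combined protocol and SAP*

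**What the plan says.** Two sections frame the comparison as non-inferiority:

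- Clinical Hypothesis: "Patients with bilateral Panoptix IOLs have non-inferior distance, intermediate, and near visual acuity compared to patients with Synergy IOLs".
- Study Objectives: PanOptix patients "will have non-inferior distance, intermediate, and near vision compared to patients with bilateral Synegy IOL".

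Two others frame it as superiority:

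- Number of Subjects assumes a difference between arms "greater than 0.05 logMAR, thus demonstrating superiority, then 155 patients per arm would be required". The other inputs follow: "The standard deviation for each measurement is 0.15 logMAR, a power of 80% and Type I error probability of 0.05".
- Evaluation Criteria: "The main objective of this study is to demonstrate superiority of distance, intermediate, and near vision with bilateral Panoptix IOLs".

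Overall Study Design carries the number forward: "155 subjects will be enrolled in each arm of the study, with 310 total subjects". Primary Clinical Endpoints names one variable, "Binocular DCNVA of Trifocal (Alcon PanOptix) versus EDOF/Bifocal (Johnson and Johnson Tecnis Synergy) at 40 cm", and attaches no hypothesis to it.

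The document states no non-inferiority margin, confidence-interval rule or order of testing, and does not say whether the 0.05 Type I error is one- or two-sided. The 0.05 logMAR is described only as a superiority difference, never as a margin.

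**The concern.** Non-inferiority and superiority have different null hypotheses, and the plan assigns both to the same comparison without saying which governs. If PanOptix proves superior on the primary endpoint, non-inferiority on that endpoint follows and the conflict does no harm. In every other case the plan has no rule, because a non-significant superiority test does not establish non-inferiority.

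Such a case is a realistic prospect. The hypothesis allows the lenses to have similar acuity, and the Background cites a post-marketing study claiming a better range of vision for Synergy. The conclusion would then depend on a framework or margin chosen with the results in view.

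**Working it through.** **Inputs.** From Number of Subjects: difference 0.05 logMAR, SD 0.15 logMAR, power 80%, Type I error 0.05, 155 per arm. Not in the document, so assumed here: the margin M, the true difference d (PanOptix minus Synergy; positive means PanOptix is worse) and the sidedness. All figures use the normal approximation for an unadjusted comparison of two means.

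**1. The plan's own figure.** n per arm = 2 × SD² × (z_α + z_β)² / difference².

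- Two-sided 0.05, 80% power: 2 × 0.15² × (1.960 + 0.842)² / 0.05² = 141.3, so 142.
- One-sided 0.05, 80% power: 111.3, so 112.
- One-sided 0.05, 90% power: 154.1, so 155. This matches the stated number but contradicts the stated 80%.

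The stated inputs therefore do not give 155. With M in place of the difference and d = 0, the same formula sizes a non-inferiority test, so the number 155 reveals neither the framework nor the sidedness.

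**2. Precision at 155 per arm.** SE = 0.15 × √(2/155) = 0.01704. The two-sided 95% CI half-width is 1.96 × 0.01704 = 0.033 logMAR.

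- Superiority needs an observed PanOptix advantage above 0.033.
- An observed difference of 0 puts the upper limit at 0.033. Superiority fails; non-inferiority passes for a margin of 0.04 and fails for 0.03.

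**3. Chance of each conclusion if the lenses are equal (d = 0).** Superiority: Φ(−d/SE − z). Non-inferiority: Φ((M − d)/SE − z).

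| | One-sided 0.025 (z = 1.960) | One-sided 0.05 (z = 1.645) |
|---|---|---|
| Superiority shown | 2.5% | 5% |
| Non-inferiority, M = 0.03 | 42.1% | 54.6% |
| Non-inferiority, M = 0.04 | 65.1% | 75.9% |
| Non-inferiority, M = 0.05 | 83.5% | 90.1% |
| Non-inferiority, M = 0.06 | 94.1% | 97.0% |

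At one-sided 0.025, M = 0.075 gives 99.3% and M = 0.10 gives above 99%.

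**4. If PanOptix truly has the planned 0.05 advantage.** Superiority power is Φ(0.05/0.01704 − 1.96) = 83.5%, so superiority is still missed about 16.5% of the time.

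**5. What 155 per arm supports for non-inferiority (one-sided 0.025).** Power depends only on M − d. The smallest M − d with 80% power is (1.960 + 0.842) × 0.01704 = 0.048 logMAR. Each of these has M − d = 0.05 and so 83.5% power: M = 0.05 with d = 0; M = 0.03 with d = −0.02; M = 0.06 with d = +0.01. The number per arm for 80% power is 142, 221 and 393 for M − d of 0.05, 0.04 and 0.03.

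**The case against.** **Scope.** The hypothesis covers three distances, two lighting conditions and visual disturbances, so a rule for DCNVA at 40 cm alone does not settle all of it. Superiority likewise implies non-inferiority only endpoint by endpoint. Both points are correct. They limit the remedy to the primary endpoint, which is where the plan puts its single primary comparison; it lists distance and intermediate acuity as secondary exploratory. The hypothesis and objectives need rewording to match.

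**Choice of margins.** The pass/fail example uses margins on either side of the 0.033 half-width. At an observed difference of 0, any margin above 0.033 passes, and power is above 99% for margins of 0.075 or more with equal lenses. So the later choice decides the result for some margins and observed differences, not all. The margins are sensitivity examples only. This does not supply the missing rule.

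**Approximate power.** The study compares patients already implanted by 4 surgeons, and an adjusted analysis would change the power somewhat. That is true, and it leaves the contradiction untouched.

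**Severity.** This is a single-visit, non-interventional study, its sizing and main objective agree on superiority, and 155 per arm gives 83.5% power for 0.05 logMAR at two-sided 0.05. One remedy is mostly wording. However, nothing says that those two sections override the hypothesis and objectives, and a framework chosen after the data are seen cannot be repaired by later wording.

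**Conclusion.** The concern holds: the plan is wrong as written and must be corrected before analysis. It contradicts itself on its main hypothesis, and as it stands that hypothesis cannot be decided on the primary endpoint whenever superiority is not shown. If the lenses are equal, that is 97.5% of the time at one-sided 0.025 (95% at one-sided 0.05). Over assumed margins of 0.03 to 0.06 logMAR, the chance of a non-inferiority conclusion at one-sided 0.025 then runs from 42.1% to 94.1%.

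The contradiction and the missing rule rest on the text alone. The percentages rest on the plan's SD of 0.15 and 155 per arm, an unadjusted comparison, and the assumed margins, true difference and sidedness.

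**What to change.** Before analysis, set one framework for binocular DCNVA at 40 cm, state the sidedness of alpha, and bring Clinical Hypothesis, Study Objectives, Number of Subjects and Evaluation Criteria into line with it.

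- **Option A, non-inferiority then superiority.** Require the upper limit of the two-sided 95% CI for PanOptix minus Synergy to lie below a margin in logMAR that the sponsor states and justifies. If it does, test superiority (upper limit below 0) in fixed sequence, at no alpha cost. Restate the power for that margin and an assumed true difference.
- **Option B, superiority only.** Change the Clinical Hypothesis and Study Objectives to superiority, and state that a non-significant result will not be reported as non-inferiority.

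Both cost wording in four places and a short analysis paragraph. Option B needs no change in N. Option A also needs a margin rationale. At one-sided 0.025, 155 per arm suffices for 80% power if margin minus true difference is about 0.048 logMAR or more. Below that, the sponsor must either state lower power or enrol more: about 221 per arm at 0.04 and 393 at 0.03. Option A's drawback is that its stated power depends on the assumed true difference. Under either option, say that distance and intermediate acuity fall outside the primary decision rule, or give them a rule of their own.

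### The lens is not assigned by the study, yet no covariate adjustment is prespecified and the plan does not say it will record or use surgeon or surgery date

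*Combined protocol and SAP*

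**What the plan says.** Overall Study Design calls the study non-interventional and describes a "two-arm comparative study of the outcomes for patients following successful, uncomplicated cataract surgery performed by 4 surgeons using similar surgical techniques". It is also "single center, bilateral, examiner blinded". Under Inclusions, item 1, patients enter "having already undergone cataract removal by phacoemulsification with a clear corneal incision in both eyes", so the lens was chosen before the study met the patient.

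Visit Schedule states that "All subjects will undergo 1 visit". At that visit "demographic information will be collected", followed by seven tests or questionnaires. Surgeon and date of surgery are not on that list. No criterion sets a minimum or maximum interval since cataract surgery; the only timing rule concerns YAG capsulotomy (Inclusions, item 6).

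The comparative aim is worded in two ways. Study Objectives says PanOptix patients "will have non-inferior distance, intermediate, and near vision compared to patients" with Synergy. Number of Subjects and Evaluation Criteria speak of superiority. The only comparison described is the one behind the sample size: a "difference between binocular targeted corrected distance, intermediate, and near visual acuity between the two arms greater than 0.05 logMAR, thus demonstrating superiority". There is no statistical analysis section and no mention of a test, model, covariates, matching, weighting or stratification.

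**The concern.** When a study does not assign treatment, the arms can differ in who was treated, by whom and how long ago. Here the surgeon may have influenced which lens was implanted, patients may be tested at different times after surgery, and the arms may differ in age. A plain difference between arms attributes all of this to the lens, and a larger sample does not remove it. The target difference is only 0.05 logMAR, so a small systematic shift is not negligible beside it.

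Both the superiority and the non-inferiority wording attribute the arm difference to the lens. Choosing covariates after the data are seen would leave the result open to the choice of model, which is why the adjustment belongs in the plan.

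**Working it through.** **Inputs from the documents.** Number of Subjects: "The standard deviation for each measurement is 0.15 logMAR, a power of 80% and Type I error probability of 0.05"; target difference 0.05 logMAR; 155 per arm. Sidedness is not stated; two-sided 0.05 is assumed below.

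**The plan's own figure.** n per arm = 2 × ((1.960 + 0.8416) × 0.15 / 0.05)² = 141.28, so 142. The stated 155 is not reproduced, but it errs on the safe side and is a separate matter. At 155 per arm:
- SE = 0.15 × √(2/155) = 0.01704
- power = Φ(0.05/0.01704 − 1.96) = Φ(0.974) = 83.5%

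**Effect of an uncorrected bias b when the lenses do not differ.** Type I error = Φ(b/SE − 1.96) + Φ(−b/SE − 1.96). The documents give no figures for imbalance, so every input to b is assumed.

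Months since surgery, with correlation r to near acuity and a between-arm imbalance of d SD: b = r × d × 0.15.
- r 0.1, d 0.1: b = 0.0015, b/SE = 0.088, error 5.1%
- r 0.2, d 0.25: b = 0.0075, b/SE = 0.440, error 7.2%
- r 0.3, d 0.5: b = 0.0225, b/SE = 1.321, error 26.2%

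Surgeon, with two pairs of equal volume using PanOptix in shares p and 1 − p, and pairs differing by 0.03 logMAR: b = 0.03 × (2p − 1).
- p 0.60: b = 0.006, b/SE = 0.352, error 6.4%
- p 0.75: b = 0.015, b/SE = 0.880, error 14.2%

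For a claim in one direction only (PanOptix superior, nominal 2.5%), b = 0.0075 gives Φ(0.440 − 1.96) = 6.4% if the bias favours PanOptix and Φ(−0.440 − 1.96) = 0.8% if it opposes it.

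**Precision cost of adjusting.** If the covariates explain a fraction R² of lens choice, adjusted SE = 0.01704/√(1 − R²), taking no gain from outcome variance explained. For months, R² = d²/(d² + 4); for surgeon, R² = (2p − 1)².
- Break-even for 80% power: R² = 1 − 141.28/155 = about 8.9%
- Months 0.25 SD: R² 1.5%, power 82.9%
- Surgeon 60/40: R² 4%, power 82.0%
- Months 0.5 SD: R² 5.9%, power 81.2%
- Surgeon 60/40 and months 0.5 SD together, if unrelated: R² 4% + 5.9% = 9.9%, power about 79.5%, before age is added
- Surgeon 75/25: R² 25%, power about 72%

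**The case against.** **The design already restricts confounding.** One center, similar techniques, uncomplicated surgery, clear media, ocular exclusions, limits on corrected acuity, astigmatism and spherical equivalent, examiner blinding and a distance-corrected primary endpoint all help. Distance correction in particular removes differences in residual refraction. This stands as a reason to expect modest bias, and the illustrations above apply no discount for it. But restriction does not balance surgeon, age or time since surgery between arms, and blinding the examiner addresses measurement, not selection.

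**The data may well exist.** A reader might infer that the study could neither detect nor adjust for an imbalance in surgeon or time since surgery. The documents do not support that. The visit list is not a full data dictionary: it also omits lens model and YAG date, which eligibility cannot be judged without. Surgeon and surgery date are probably in the center's records. The gap is that the plan does not commit to recording or using them.

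**No unadjusted analysis is actually specified.** This is correct. A sample-size paragraph is not an analysis plan, and the documents neither adopt nor rule out adjustment. The point is that nothing is prespecified and the one comparison described is unadjusted.

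**The size is hypothetical.** This is also correct. Nothing in the documents links surgeon or time since surgery to distance-corrected near acuity, and the 0.03 logMAR surgeon difference, 60% of the target, has no source. The choice of covariates is partly judgement too: toric lenses and earlier YAG capsulotomy are permitted and could be argued for.

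**Conclusion.** The point holds as a gap in the plan. A comparison of arms that the study did not form is meant to support a conclusion about the lenses, with no prespecified adjustment and no stated intention to record or use surgeon or surgery date.

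The documents do not show that an imbalance exists or which way it would act, so this is not evidence that the result will be biased. Under the assumed inputs, the central cases raise a two-sided 5% error to 6.4% and 7.2%. The mild case is harmless at 5.1%, and 26.2% needs the extreme correlation and the extreme imbalance together. These rates do not carry over directly to the non-inferiority wording, although a bias would shift the estimate there as well. It should be corrected, mainly because doing so is cheap. Confidence is medium.

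**What to change.** - Record the surgeon and the second-eye surgery date from the chart.
- Prespecify as primary a linear regression of binocular distance-corrected near acuity at 40 cm on lens, adjusted for age, surgeon (4 levels) and months since second-eye surgery. Report the adjusted difference with its 95% CI, and give the unadjusted difference as a sensitivity analysis.
- Tabulate lens by surgeon, and months since surgery by lens. State in advance that, if surgeons largely use one lens, the surgeon-adjusted estimate will be reported as weakly identified.
- Describe the result as an adjusted association.

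The cost is two routine data fields, a paragraph of text and some precision. The margin above 80% power covers modest imbalance but not every case: it is just used up in the combined example, and clearly exceeded at a 75/25 surgeon split, which is also where the unadjusted error would be 14.2%. Outcome variance explained by the covariates would recover some of this. Unmeasured reasons for choosing a lens remain whatever model is used.

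### The protocol states both non-inferiority and superiority, and its 155 per arm does not follow from the superiority inputs it gives

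*Combined protocol and SAP*

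**What the plan says.** **Sample size.** Number of Subjects takes as its assumption "the difference between binocular targeted corrected distance, intermediate, and near visual acuity between the two arms greater than 0.05 logMAR", and the same sentence goes on to the sample size: "greater than 0.05 logMAR, thus demonstrating superiority, then 155 patients per arm would be required, for a total of 310 patients". The other inputs follow: "The standard deviation for each measurement is 0.15 logMAR, a power of 80% and Type I error probability of 0.05". The section cites an online sample size calculator. It does not say whether the test is one- or two-sided, and it gives no dropout allowance, multiplicity adjustment or margin. Overall Study Design repeats the number: "155 subjects will be enrolled in each arm of the study, with 310 total subjects".

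**Hypothesis.** Clinical Hypothesis reads "Patients with bilateral Panoptix IOLs have non-inferior distance, intermediate, and near visual acuity compared to patients with Synergy IOLs". Study Objectives says that PanOptix patients "will have non-inferior distance, intermediate, and near vision compared to patients with bilateral Synegy IOL". Evaluation Criteria says something different: "The main objective of this study is to demonstrate superiority of distance, intermediate, and near vision with bilateral Panoptix IOLs".

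**Endpoint.** Primary Clinical Endpoints has one entry: "Binocular DCNVA of Trifocal (Alcon PanOptix) versus EDOF/Bifocal (Johnson and Johnson Tecnis Synergy) at 40 cm". Corrected distance acuity (BCDVA) and corrected intermediate acuity (DCIVA) appear under Secondary Exploratory Clinical Endpoints.

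**The concern.** Three things that should agree do not.

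1. The stated inputs do not produce the stated number, so a reader cannot tell which test the study was sized for.
2. The hypothesis is non-inferiority in two places and superiority in two others. No margin is given, and nothing says the two are to be tested in sequence.
3. The sizing sentence and the main objective cover three acuities, but only near acuity at 40 cm is primary. No rule says whether success needs one acuity or all three.

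The second matters most. A difference near zero could be reported as success under Clinical Hypothesis and would be a failure under Evaluation Criteria. Unless one is fixed beforehand, the criterion can be chosen after the data are seen.

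**Working it through.** **Inputs** (Number of Subjects): difference d = 0.05, SD = 0.15, power 80%, type I error 0.05. Allocation is equal (Overall Study Design). Sidedness is not stated, so both are shown.

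**Step 1: the plan's own figure.** For two means, n per arm = 2 × (SD/d)² × (z_α + z_β)², with 2 × (0.15/0.05)² = 18.

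- Two-sided 0.05: 18 × (1.9600 + 0.8416)² = 141.28, so 142 (143 by t-test).
- One-sided 0.05: 18 × (1.6449 + 0.8416)² = 111.29, so 112 (also 112 by t-test).

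Neither is 155, which is 12–13 above the two-sided requirement and 43 above the one-sided one.

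**Step 2: routes that do reach 155.**

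- Equivalence by two one-sided tests, margin ±0.05, true difference 0: 18 × (1.6449 + 1.2816)² = 154.15, so 155. This is the only route found that leaves all four numbers unchanged. The protocol never mentions equivalence, so its use is an inference.
- One-sided 0.05 with 90% power: the same arithmetic, 155, but a different power.
- An unstated allowance, for example 142/0.92 = 154.3, so 155. (143/0.92 = 155.4 would give 156.)
- A difference of 0.048, two-sided: 153.3 by the normal formula, 155 by t-test.

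**Step 3: what 155 per arm delivers for superiority.** SE = 0.15 × √(2/155) = 0.01704. If the true difference is 0.05, power by t-test is 83.3% two-sided or 90.0% one-sided, for one comparison.

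**Step 4: how far the two hypotheses diverge for DCNVA.** The 95% CI half-width is 1.968 × 0.01704 = 0.0335. The documents give no margin; 0.05 is assumed here for illustration.

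- Non-inferiority is met if PanOptix is observed to be worse by less than 0.05 − 0.0335 = 0.0165.
- Two-sided superiority needs PanOptix observed to be better by more than 0.0335.
- Any result between those limits meets one criterion and fails the other.
- At a true difference of 0, the probability of meeting non-inferiority (one-sided 0.025) is 0.833. The probability of showing PanOptix superior is 0.025.

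**Step 5: dependence on the margin.** Non-inferiority n per arm = 2 × (0.15/margin)² × (z_α + 0.8416)², at 80% power and true difference 0:

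| Assumed margin (logMAR) | One-sided 0.025 | One-sided 0.05 |
|---|---|---|
| 0.04 | 221 | 174 |
| 0.05 | 142 | 112 |
| 0.10 | 36 | 28 |

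The smallest margin that 155 per arm support is 0.01704 × 2.8016 = 0.0477 at one-sided 0.025, or 0.01704 × 2.4865 = 0.0424 at one-sided 0.05.

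**Step 6: the other reading of the 0.05.** If 0.05 is a bound to be exceeded rather than the assumed true difference, 155 per arm reach 80% power only at a true difference of 0.05 + 0.0477 = 0.0977 (two-sided) or 0.05 + 0.0424 = 0.0924 (one-sided).

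**The case against.** **The number errs on the safe side.** An excess of 12–13 per arm over the two-sided requirement weakens no conclusion, and an ordinary unstated allowance could explain it. For instance, 141.28 × 1.10 = 155.4, which is 155 to the nearest whole number. The cited calculator's method cannot be seen in the documents. This stands: the arithmetic alone is a traceability point, and the equivalence formula is no better evidenced than inflation.

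**The contrast is for one component only.** Both the hypothesis and the main objective also require fewer visual disturbances, and both span three acuities and two lighting conditions. Meeting non-inferiority on one acuity is therefore not overall success. This stands as a limit on the 83% against 2.5% contrast, which describes DCNVA alone. If all three acuities had to meet a 0.05 margin and were independent, the chance would be 0.833³ = 0.58; at assumed correlations of 0.5 and 0.8 it is about 0.66 and 0.73. The two readings would still be far apart.

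**Non-inferiority and superiority can be tested in sequence.** They can, but the protocol states no such sequence and no margin, so the contradiction remains.

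**The SD is given for each measurement, so near acuity is sized.** This is fair for power on DCNVA. It does not say which acuities the confirmatory claim rests on.

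**The 0.05 most naturally reads as an assumed true difference.** Probably so, and the power in Step 3 uses that reading. The wording still allows the other one.

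**Conclusion.** The concern holds. The hypothesis conflict is the substantive part: the current text contradicts itself on what counts as success, and with an assumed 0.05 margin the two criteria disagree over a band of observed differences about 0.05 logMAR wide (0.0165 worse to 0.0335 better).

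The sample size of 155 does not follow from the stated superiority inputs, but the study is not underpowered for superiority on DCNVA at 40 cm, provided 0.05 is the true difference and the SD is 0.15. Whether 155 is enough for non-inferiority cannot be judged until a margin is stated. How the sponsor obtained 155 cannot be established from the documents. This should be corrected, and confidence in the finding is high.

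**What to change.** 1. Make Clinical Hypothesis, Study Objectives, Number of Subjects and Evaluation Criteria state one hypothesis for the primary endpoint.
2. If it is superiority, restate the sizing, for example: *155 per arm give 83% power, at two-sided alpha 0.05, to detect a true difference of 0.05 logMAR (SD 0.15) in binocular DCNVA at 40 cm.* This describes the existing number and does not recover its derivation. Alternatively, give the actual basis (sidedness, allowance or equivalence) and reconcile it with the hypothesis. Either way, say whether 0.05 is the assumed true difference or a bound to be exceeded.
3. If it is non-inferiority, state and justify a margin and the one-sided alpha, and check 155 against them.
4. Tie the sizing sentence and the confirmatory acuity claim to DCNVA at 40 cm, and name the lighting condition, which the primary endpoint leaves open. BCDVA and DCIVA stay secondary exploratory, as listed. If a confirmatory claim on all three acuities is wanted, state the success rule and its power.

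**Cost.** Keeping superiority on DCNVA needs wording changes only and no added patients. Choosing non-inferiority requires a justified margin. More than 155 per arm would be needed for a margin below about 0.048 logMAR at one-sided 0.025, or below about 0.042 at one-sided 0.05. The price of step 4 is that distance and intermediate acuity are no longer presented as powered claims.

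### No minimum time since second-eye surgery is set, recorded or adjusted for, so unequal intervals between the non-randomised arms could bias halo, glare and satisfaction comparisons

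*Combined protocol and SAP*

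**What the plan says.** The list of inclusions contains one waiting time, item 6: "Minimum of two weeks post YAG capsulotomy to treat PCO". For the cataract surgery, item 1 describes subjects as "having already undergone cataract removal by phacoemulsification with a clear corneal incision in both eyes" and gives no interval from either operation to the visit.

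Under Visit Schedule, "All subjects will undergo 1 visit". The procedures named there are demographics, refraction, acuities, questionnaires, the defocus curve, and halo and glare testing. Date of surgery is not among the items to be collected.

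The only other statement about time is under Duration, "3 months or longer to meet required enrollment", which describes how long recruitment runs and not how long after surgery a subject is examined.

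Overall Study Design says: "This is a non-interventional prospective, single center, bilateral, examiner blinded, two-arm comparative study". The lenses are already in place at enrolment, so the study does not assign them. The document mentions no matching, stratification or covariate adjustment.

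Two criteria limit refraction in both arms: "Residual refractive astigmatism ≤ 0.75 diopters" (item 7) and "Post-operative refractive spherical equivalent from +0.50 to -0.50 SE" (item 8).

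**The concern.** Item 6 accepts that an eye needs time after a procedure before it is tested. The implantation under study has no such rule. As written, the criteria admit any interval after second-eye surgery, short or long, provided the other conditions are met on the day.

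In a randomised trial with a scheduled visit the interval would be alike in the two arms by design. Here nothing makes it so. If patients with one lens were operated on more recently on average, the comparison mixes lens with time since surgery. A single visit gives no later assessment that could separate them, and masking the examiner does not balance the interval.

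The outcomes most exposed are those that may change as patients adapt: halo and glare complaints and satisfaction. Uncorrected acuity is exposed to a lesser degree. Reduced glare, halos and starbursts form part of the clinical hypothesis and of the main objective under Evaluation Criteria, so a bias there touches a claim the study is meant to support.

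**Working it through.** **Is there a rule anywhere?** Each statement that could fix the interval, side by side:

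| Place | What it fixes | Time since cataract surgery? |
|---|---|---|
| Inclusion 1 | Both surgeries done | No interval |
| Inclusion 6 | Two weeks after YAG | Different procedure |
| Inclusions 7 and 8 | Refraction at or within limits | No |
| Inclusions 4 and 5; exclusions 5 and 10 | Acuity, clear media, no inflammation | Indirect only |
| Visit Schedule | One visit | No window |
| Duration | Recruitment period | No |

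No minimum or maximum is set from first-eye or second-eye surgery.

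**How large could the bias be?** The document has no figure of its own to reproduce on this point. It gives 155 per arm and a Type I error of 0.05. (The 155 is taken as stated. The stated difference of 0.05 logMAR, SD of 0.15 and 80% power give 142 per arm, two-sided; that is a separate matter with no bearing here.) Everything else below is assumed.

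Assumptions: 40% bothered by halos overall, no true difference between lenses, a two-sided test, bother higher by *s* in recently operated patients, and a share of recent patients that differs by *w* between arms.

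Spurious difference: b = s × w.

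Standard error of the difference: √(2 × 0.40 × 0.60 / 155) = √(0.48 / 155) = 0.0556.

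False-positive rate: 1 − Φ(1.96 − b/SE) + Φ(−1.96 − b/SE).

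| s | w | b | b/SE | False-positive rate |
|---|---|---|---|---|
| any | 0 | 0 | 0 | 5.0% |
| 0.10 | 0.10 | 0.01 | 0.18 | 5.4% |
| 0.10 | 0.20 | 0.02 | 0.36 | 6.5% |
| 0.10 | 0.40 | 0.04 | 0.72 | 11% |
| 0.15 | 0.40 | 0.06 | 1.08 | 19% |
| 0.20 | 0.60 | 0.12 | 2.16 | 58% |

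Small imbalances do little harm. The error rate becomes serious only when the arms differ widely in recency and symptoms also change materially with time. The direction is not known: the same mechanism could hide a real difference as well as create a false one.

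**The case against.** The strongest reply has four parts.

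*Other criteria already screen unsettled eyes.* Clear media, corrected acuity of 0.10 logMAR or better, no current inflammation, and the limits on astigmatism and spherical equivalent would together remove some very early eyes. This stands in part. A reader might infer that refraction is as exposed as symptoms, but items 7 and 8 bound it in both arms, and manifest refraction is measured at the same visit as the acuities. What these filters do not control is time to adapt, or long intervals.

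*The primary endpoint is distance-corrected near acuity at 40 cm.* This also stands. A reader might infer that the primary comparison is confounded to the same degree, and the documents do not support that: residual refractive error is corrected before measurement. That it is less affected is a judgement from how it is measured, not a figure in the plan. The exposed endpoints are listed as secondary and exploratory, although fewer glare and halo complaints also appear in the main objective.

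*No imbalance is shown.* True. A reader might infer that the arms do differ in time since surgery, or that the error rate must be well above 5%. The document gives no surgery dates, halo rate or time course, and with equal timing the bias is zero. The point is that the plan neither ensures equal timing nor collects what would show it.

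*Routine practice would avoid very early testing.* The document does not say so, and an unwritten custom would not make the interval alike in the two arms.

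**Conclusion.** The concern holds in a limited form. The plan sets a wait after YAG and none after the lens surgery, and does not provide for recording or adjusting for the interval. In a non-randomised, single-visit comparison this permits bias in the halo and glare, satisfaction and, less so, uncorrected acuity results.

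The calculated range, from no inflation of the 5% error rate to about 58%, concerns the halo comparison only. It rests wholly on the assumed 40% bother rate, a symptom difference of up to 20 points, and an imbalance of up to 60 points in the share of recent patients. It shows what the design allows and does not predict what will occur. The omission should be corrected before enrolment, because adjustment afterwards works poorly if the two arms' intervals barely overlap.

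**What to change.** 1. Add an inclusion criterion that the study visit takes place at least a stated minimum interval after second-eye surgery, the same in both arms. The sponsor should choose and justify the length; the documents give no basis for a particular figure.
2. Record days since second-eye surgery from the chart.
3. Report the distribution of that interval by arm, so that readers can judge balance and overlap.
4. Pre-specify it as a covariate in the symptom, satisfaction and uncorrected acuity comparisons.

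A minimum alone would not equalise the arms, which is why items 2 to 4 are needed with it.

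The cost is one eligibility line, one chart field and one covariate. Some recently operated patients would wait for their single visit, which is tolerable because recruitment is already open-ended. An upper limit or a common surgery-date window is optional. It would tighten comparability, but patients outside it are lost, not merely delayed, and 155 per arm could become harder to reach.
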